6.4.5 Schedule of Events

The schedule of activities specific to this clinical study are described in the preceding sections and are summarized in Table 2.

Table 2. Clinical Study Specific Tests/Activities and Procedures

Visit	Time of Consent (may be at time of baseline visit)	Baseline Visit(s)	Procedure Visit	Pre-discharge	6-month Visit (180 days ± 90 days post procedure)	12-month Visit (360 days ± 90 days post procedure)	Unscheduled Visit
Study Activity							
Eligibility check	X	(X)	(X)				
Informed Consent	X						
Demographics		X					
Physical examination		X					
LVEF and LAD assessment		X					
Cardiovascular Disease History		X					
Arrhythmia History		X					
12-Lead ECG		X		X	(X)	(X)	(X)
Anticoagulant Medication		X	X				
Antiarrhythmic Medication		X	X	X	X	X	(X)
EQ-5D/AFEQT or EQ-5D/HADS questionnaires		X			X	X	
Mapping of cardiac structures and electroanatomical map(s)			X				
RF Ablation			X				
Obtain Procedure USB			X				
48-hour Holter-monitoring (PersAF only)						X	(X)
ICD interrogation (VT only)				(X) ^a	(X) ^a	(X) ^a	(X) ^a
Other arrhythmia monitoring and source documentation					(X)	(X)	(X)
Healthcare Utilization					(X)	(X)	(X)
Repeat Ablation				(X)	(X)	(X)	(X)
Protocol Deviation	(X)	(X)	(X)	(X)	(X)	(X)	(X)
Withdrawal	(X)	(X)	(X)	(X)	(X)	(X)	(X)
Adverse Events	(X)	(X)	(X)	(X)	(X)	(X)	(X)
Death	(X)	(X)	(X)	(X)	(X)	(X)	(X)

(X) If applicable

^a Non-SJM ICDs may require in-office interrogation

6.5 Core Laboratory

A core lab will be used for the collection, interpretation, and collation of data collected from Holter monitoring.

Clinical Investigation Plan

The core lab will provide independent review of this data by appropriately trained personnel using standardized procedures to interpret Holter monitor tracings for adjudication of atrial arrhythmias. Findings will be communicated to the investigator and to Abbott. The core lab's adjudication findings will be used for analysis.

7 ADVERSE EVENTS

To comply with worldwide standards and guidelines on clinical investigation adverse event reporting, the Sponsor has adopted uniform and worldwide applicable standard definitions and reporting timelines to be used and adhered to by the investigators.

7.1 Definitions

7.1.1 Adverse Event

An adverse event (AE) is any untoward medical occurrence, unintended disease or injury, or untoward clinical signs (including abnormal laboratory findings) in subjects, users or other persons, whether or not related to the medical device used in this study.

Note 1: This definition includes events related to the medical device(s) used in this study.

Note 2: This definition includes events related to the procedures involved.

Note 3: For users or other persons, this definition is restricted to events related to medical devices used in this study.

7.1.2 Serious Adverse Event

If the AE meets any of the criteria below, it is regarded as a serious adverse event (SAE).

- a) Led to a death,
- b) Led to a serious deterioration in health of the subject, that either resulted in
 1. a life-threatening illness or injury, or
 2. a permanent impairment of a body structure or a body function, or
 3. in-patient hospitalization or prolongation of existing hospitalization, or
 4. medical or surgical intervention to prevent life threatening illness or injury or permanent impairment to a body structure or a body function.
 5. chronic disease
- c) Led to fetal distress, fetal death or a congenital abnormality or birth defect.

Note: A planned hospitalization for pre-existing condition, or a procedure required by the CIP, without a serious deterioration in health, is not considered to be an SAE.

Clinical Investigation Plan

7.2 Device Relationship

Determination of whether there is a reasonable possibility that a device used in this study caused or contributed to an AE is to be **determined by the Investigator** and recorded on the appropriate CRF form. Determination should be based on assessment of temporal relationships, evidence of alternative etiology, medical/biologic plausibility, and patient condition (pre-existing condition).

7.2.1 Adverse Device Effect (ADE)

The following definition will be used to categorize non-serious procedure or device-related AEs:

- An adverse event related to the use of a device used in this study.
- This definition includes adverse events resulting from insufficient or inadequate instructions for use, deployment, implantation, installation, or operation, or any malfunction of the medical device used in this study.
- This definition includes any event resulting from the use error or from intentional misuse of the medical device used in this study.

7.2.2 Serious Adverse Device Effect (SADE)

The following definition will be used to categorize serious procedure or device-related AEs:

- Adverse device effect that has resulted in any of the consequences characteristic of a serious adverse event.
- This definition includes events related to the medical device used in this study.

7.3 Safety Reporting

7.3.1 Adverse Event Reporting

Safety surveillance and reporting starts for each subject as soon as the subject is enrolled in the clinical study and will continue until the subject's 12-month follow-up visit has been performed, the subject is deceased, the subject concludes participation in the clinical study, or the subject withdraws from the clinical study. All device effects regardless of severity (ADEs and SADEs) and cardiovascular SAE data, will be collected throughout the time period defined above and will be reported to the Sponsor on the Adverse Event CRF. Additional information with regard to an adverse event and death should be updated within the appropriate CRF.

Recurrence of AF, AFL, or AT in subjects treated for PersAF or recurrence of VT in subjects treated for VT are not considered reportable adverse events unless they occur in severity, frequency, or other manner that is significantly worse than the subject's baseline condition. Recurrence of arrhythmia will be reported as part the descriptive endpoints and will be reported on the Follow-Up Visit CRF.

Unchanged, chronic, non-worsening or pre-existing conditions are not AEs and should not be reported.

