4.1.3 Additional descriptive endpoints

Additional descriptive endpoints include:

- Change in quality of life (QOL) at 6 and 12 months after receiving HD Grid mapping and RF ablation relative to baseline: defined as change in quality of life assessed in validated QOL surveys (EQ-5D and AFEQT for subjects with PersAF, EQ-5D and HADS for subjects with VT)
- Rate of periprocedural and immediate post procedural (48hrs) procedure- or device- related adverse events in all subjects in whom the HD Grid is inserted (regardless of RF energy delivery).
- Rate of procedure- or device-related adverse events and cardiovascular serious adverse events in all subjects in whom the HD Grid is inserted (regardless of RF energy delivery) through 30 days post study procedure.
- Proportion of VT subjects who receive HD Grid mapping and RF energy delivery free from recurrence of sustained monomorphic VT and new or increased dose of class I/III AAD, and free from recurrence of sustained monomorphic VT on or off class I/III AADs at 12-month follow-up outside the blanking period.
- Rate of repeat ablations after study procedure during 12-month follow up defined as proportion of subjects without an additional ablation procedure to treat indicated cardiac arrhythmia (outside blanking period, if applicable).
- For subjects treated for PersAF:
 - Proportion with atypical atrial flutter (AFL) identified during procedure
 - Of those receiving HD Grid mapping and RF ablation for AFL: Utility of HD Grid specific to the identification and treatment of atypical AFL (as defined in section 4.1.2), including role of HD wave relative to along-the-spline maps in identifying ablation target(s), and time of RF application to terminate atypical AFL

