8.2.2 Analysis Methodology

The endpoints will be summarized descriptively based on available data or measurements in the analysis population. No formal hypothesis testing will be performed.

In general, continuous variables will be summarized with the numbers of observations, means with standard deviations, quartiles, minimums, maximums, and 95% confidence intervals for the means as per the table mockups.

Categorical variables will be summarized with subject counts and percentages/rates, and where specified in the table mockups, with exact 95% Clopper-Pearson confidence intervals.

All pre-defined adverse events will be captured. Only adverse events that occur after HD Grid catheter is inserted (after enrollment) will be analyzed, as defined in the safety analysis population. Tables will be created that show incidences of all ADEs. Cardiovascular serious adverse events will be analyzed and reported in a similar manner as ADEs.

Survival analysis will be conducted to analyze time-to-event variables. Events occurring during the 90 days following the ablation procedure for PersAF subjects (90-day blanking period) or 14-day blanking period following the ablation procedure for VT subjects will not be counted as an effectiveness outcome failure. Subjects without events will be censored at their last known event-free time point. Subjects withdrawn or otherwise lost-to-follow-up during the follow-up period will be censored at their last known visit. Survival data will be presented using the Kaplan-Meier product limit method.

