11.3 Source Documentation

Regulations and GCP require the Investigator to maintain information in the subject's original medical records that corroborates data collected on the CRFs. In order to comply with these regulatory requirements/GCP, the following information should be included in the subject record at a minimum and if applicable to the clinical study:

- Medical history/physical condition of the subject before involvement in the clinical study sufficient to verify CIP entry criteria
- Dated and signed notes on the day of entry into the clinical study referencing the Sponsor, CIP number, subject ID number and a statement that informed consent was obtained
- Dated and signed notes from each subject visit (for specific results of procedures and exams)
- Adverse events reported and their resolution, including supporting documents, such as discharge summaries, catheterization laboratory reports, ECGs, and lab results including documentation of site awareness of SAEs and of investigator assessment of device relationship for SAEs.
- CIP-required laboratory reports and 12-lead ECGs, reviewed and annotated for clinical significance of out of range results (if applicable). It is acceptable to have labs and/or ECGs reviewed and annotated in the electronic medical record system for site's that have these capabilities. For those sites that do not have such capability, the labs and ECGs should be printed and signed by the investigator.
- Notes regarding CIP-required and prescription medications taken during the clinical study (including start and stop dates)
- Subject's condition upon completion of or withdrawal from the clinical study
- Any other data required to substantiate data entered into the CRF

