15.1.1 Risks Associated with Participation in this Clinical Study

Risks to subjects enrolled in this clinical study include those risks currently associated with other commercially available electrophysiology diagnostic procedures and RF catheter ablation procedures. The risks of the procedure are related primarily to mechanical injury to the heart and vessels from catheter manipulation and thermal injury due to RF current delivery, including the risk of thromboembolism and myocardial perforation, especially for ablations in the left atrium.

For those procedures where the physician applies sedation or anesthesia, the standard risks of anesthesia also exist and include allergic reactions, pneumonia, aspiration pneumonitis, atelectasis, prolonged sedation, other medical complications and in very rare cases, death.

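### The safety endpoints count procedure- or device-related events, but the definitions, causality assessment, collection rule and tabulation cover only device effects and cardiovascular SAEs

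*Combined protocol and SAP*

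**What the plan says.** Section 4.1.3 sets two safety endpoints. The first is the "Rate of periprocedural and immediate post procedural (48hrs) procedure- or device- related adverse events in all subjects in whom the HD Grid is inserted". The second, running to 30 days, is the "Rate of procedure- or device-related adverse events and cardiovascular serious adverse events in all subjects in whom the HD Grid is inserted". Both numerators include procedure-related events.

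The sections that would supply those numerators read as follows.

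- **Causality (7.2).** The investigator makes one judgement: "Determination of whether there is a reasonable possibility that a device used in this study caused or contributed to an AE".
- **Source records (11.3).** The minimum list asks for "investigator assessment of device relationship for SAEs".
- **Categories (7.2.1, 7.2.2).** The lead-ins say the two definitions categorize AEs related to the procedure or a device, non-serious and serious respectively. The first ADE bullet then reads "An adverse event related to the use of a device used in this study", and a SADE is an adverse device effect with serious consequences.
- **Collection (7.3.1).** "All device effects regardless of severity (ADEs and SADEs) and cardiovascular SAE data, will be collected throughout the time period defined above". Section 7.3.2 adds a reporting deadline for all cardiovascular SAEs, whatever their cause.
- **Tabulation (8.2.2).** "Tables will be created that show incidences of all ADEs", with cardiovascular SAEs handled in a similar way.

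Section 15.1.1 gives mechanical and thermal injury as the primary procedural risks. Separately, for cases done under sedation or anesthesia, it says that the "standard risks of anesthesia also exist and include allergic reactions, pneumonia, aspiration pneumonitis, atelectasis, prolonged sedation", among others.

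**The concern.** A rate is only as complete as the reporting rule behind its numerator. Here the endpoint is defined on two relationships, to the procedure and to a device, while the operative text assesses one. A site that follows the definition bullets would have no instruction to report, say, an aspiration pneumonitis after anesthesia: it is not cardiovascular, and no device caused it. A site that follows the lead-in would report it.

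Two things are at stake. The published figure could be lower than the quantity it is labelled as, and part of any difference between sites could reflect how they read section 7.2.1. Unreported minor events are also hard to recover later, since section 10.4 relies on centralized data review and leaves on-site monitoring to the sponsor's discretion.

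**Working it through.** The documents state no safety rate, so there is no figure to reproduce. The check is whether each step covers what the endpoints count.

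**Step 1. Which relationship does each step cover?**

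| Step | Section | Device | Procedure |
|---|---|---|---|
| Endpoint definition | 4.1.3 | yes | yes |
| ADE/SADE lead-ins | 7.2.1, 7.2.2 | yes | yes |
| ADE/SADE definitions | 7.2.1, 7.2.2 | yes | no |
| Investigator causality | 7.2 | yes | not stated |
| Source requirement | 11.3 | yes | not stated |
| Collection | 7.3.1 | yes | only through cardiovascular SAEs |
| Tabulation | 8.2.2 | yes | only through cardiovascular SAEs |

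Note 2 of section 7.1.1 places procedure-related events within the general AE definition, but 7.3.1 does not ask for all AEs.

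**Step 2. What happens to each class of event?**

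- (a) Device-related, any severity: collected.
- (b) Cardiovascular SAE related to the procedure but not to a device: collected. The 30-day endpoint counts it as a cardiovascular SAE. The 48-hour endpoint has no such clause, so the event counts there only if someone judges it procedure-related, and no such judgement is described.
- (c) Non-serious, procedure-related, not device-related: collected only if the 7.2.1 lead-in overrides the definition below it.
- (d) Serious, non-cardiovascular, procedure-related, not device-related: collected only on the same broad reading of 7.2.2.

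The gap is (c) and (d), plus the missing classification in (b). Events before catheter insertion fall outside the analysis on either reading (8.2.2).

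**Step 3. How wide is "a device"?** Table 1 in section 2.2.1 lists no ablation catheter or sheath, but the text after it allows other commercial tools. Whether an RF-catheter or sheath injury is an ADE is therefore open, and some access-site and thermal injuries could fall in (a) or in (c)/(d) depending on the site's reading.

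**Step 4. Direction and size.** The safety denominator in 8.1 is fixed by consent and catheter insertion. A subject whose only countable event is not collected leaves the numerator and stays in the denominator, so non-collection can only lower the rate.

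For illustration, let p be the share of subjects whose only event is in (c) or (d), and r the share of those reported under the broad reading. Subjects missed = 500 × p × (1 − r). The documents give neither p nor r. Assume p between 1% and 4%:

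- r = 0, p = 1%: 500 × 0.01 = 5 subjects; 5/500 = 1.0 percentage point.
- r = 0, p = 4%: 500 × 0.04 = 20 subjects; 20/500 = 4.0 percentage points.
- r = 1: 0 subjects, whatever p is.

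Section 4 evaluates all endpoints separately for PersAF and VT, so the pooled 500 is not a planned denominator. In a cohort of n subjects, k missed subjects cost 100 × k/n points, which exceeds 100 × k/500 because n is below 500.

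**The case against.** A reader might infer that the plan excludes procedure-related events, and that this part of the numerator is largely uncollected. The documents do not support that. The 7.2.1 and 7.2.2 lead-ins apply ADE and SADE to procedure-related events; read through them, collection and tabulation match the endpoints. The conflict is internal wording, not a clean exclusion. Cardiovascular SAEs are collected whatever the cause, so serious perforation and thromboembolism are not lost. The primary risks in 15.1.1 arise from catheters and RF delivery, and a device used in the study can fairly be read to include an ablation catheter; the anesthesia risks are separate and conditional.

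Other points also count against a strong claim. The CRFs are under separate cover (Appendix II) and the table mockups cited in 8.2.2 are not public, so a procedure-relationship field or table can be neither confirmed nor excluded. Sections 6.3 to 6.4.2 and Table 2 schedule AE recording without a device restriction. Section 3.2 adds an independent sponsor assessment, and 8.2.2 says pre-defined AEs will be captured.

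All of this stands as a limit on the claim. It does not close the gap. A CRF field cannot classify an event the site was not asked to report; section 3.2 states no procedure-relationship criterion and nothing shows it reaches unreported events; and no list of pre-defined events appears in the public text. The lead-ins show intent, but the bullets beneath them are what a site would apply to an individual event.

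**Conclusion.** The concern holds as an inconsistency between the endpoint definition and the steps that feed it. Non-serious or non-cardiovascular procedural events unrelated to a device may be missed or reported unevenly, and the 48-hour endpoint lacks a stated rule for classing cardiovascular SAEs as procedure-related.

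The bias from non-collection is downward and of unknown size. The illustrative loss of 0 to 20 subjects rests on an assumed 1% to 4% event share and on a reporting share anywhere from none to all; it is not an estimate. The classification gap in the 48-hour endpoint leaves that rate indeterminate rather than biased in a known direction.

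Should-fix: these are additional descriptive endpoints with no hypothesis test and no pass/fail criterion, and the CRFs have not been seen.

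**What to change.** - **7.3.1:** collect all procedure- or device-related AEs, serious or not and cardiovascular or not, at least through 30 days, plus cardiovascular SAEs, to match 4.1.3.
- **7.2:** have the investigator record relationship to the procedure as well as to a device. Carry this into 11.3.
- **7.2.1 and 7.2.2:** reconcile the lead-ins with the definitions, and state whether devices used in the study include ablation catheters and accessories outside Table 1.
- **8.2.2:** tabulate procedure-related and device-related events, by PersAF and VT cohort.

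The cost is CIP wording, an AE CRF field if none exists, and a short retraining note for sites. The downside is somewhat more AE entry and probably a less favourable reported rate. No treatment changes.

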7.3.2 SAE Reporting

The investigator should report all cardiovascular SAEs to the Sponsor as soon as possible but no later than outlined below.

Clinical Investigation Plan

Clinical Site	Reporting timelines
All Sites	SAEs must be reported to the Sponsor no later than 3 calendar days from the day the site personnel became aware of the event or as per the investigative site's local requirements, if the requirement is more stringent than those outlined.

The date the site staff became aware the event met the criteria of an SAE must be recorded in the source document. The Investigator will further report the SAE to the local IRB/EC according to the institution's IRB/EC reporting requirements.

An offline form will be made available to allow the investigator to report SAEs in the event the entry cannot be made in the EDC. This does not replace the EDC reporting system. All information must still be entered in the EDC system as soon as feasible.

7.3.3 Complaints

During the study, the investigator will be responsible for reporting all complaints they became aware of. A complaint is defined as any written, electronic or oral communication that alleges deficiencies related to the identity, quality, durability, reliability, safety, effectiveness or performance of a device after it is released for distribution.

The investigator must notify the Abbott Product Performance Group (PPG) by submitting the information on the device via email to [contact] or by [contact] as soon as possible after becoming aware of the complaint. This information will not be collected on a CRF for the study.

The Sponsor will investigate all complaints according to the Sponsor's post market surveillance/customer complaint procedures and will report it to the appropriate regulatory body if necessary

8 STATISTICAL CONSIDERATIONS

The following section describes the statistical methods for the clinical study. The study will investigate the outcomes of RF ablation after, and the utility of electroanatomical mapping with HD Grid and EnSite Precision with HD Wave. The study is a prospective, multicenter, unblinded observational study.

Endpoints described in Section 4.1 will be analyzed and reported using summary statistics. No hypothesis tests will be performed. Additional analysis using data collected in this study, including data from the recorded EnSite Precision case, may be performed during or after completion of the 12-month follow-up period for all subjects.

A one-sided 0.025 level of significance or two-sided 0.05 level of significance will be used to declare statistical significance, as applicable. Multiplicity adjustments will not be made unless specified below.

Statistical analysis will be performed using SAS version 9.3 or higher, or other analysis tools/software as necessary.

8.1 Analysis Populations

[REDACTED]

[REDACTED]

Clinical Investigation Plan

A safety analysis population will be used for safety-related descriptive endpoints. All subjects who have signed informed consent and have the HD Grid catheter inserted will be included in the safety analysis population regardless of protocol violations, as this is the most conservative analysis.

